1 ABBREVIATIONS

Арр	Application
CI	Chief Investigator
COPD	Chronic Obstructive Pulmonary Disease
e-Consent	Electronic consent
EDC	Electronic Data Capture
ICH	International Conference on Harmonisation
LH	Lindus Health
GCP	Good Clinical Practice
GP	General Practitioner
PIS	Patient Information Sheet
REC	Research Ethics Committee
RCT	Randomised Clinical Trial
SAP	Statistical Analysis Plan
QOF	Quality and Outcome Framework

Protocol: 22 November 2022, v2.0

2 STUDY SYNOPSIS

Title	A randomised controlled trial to evaluate the impact of supportive text messages from GP practices on self-reported symptoms and inhaler adherence in patients with asthma and/or chronic obstructive pulmonary disease (COPD) who have been prescribed a preventer (daily) inhaler (Inhaler Trial)
Short Title	A research study to explore the impact of GP support via text messages to patients with asthma and/or COPD
Protocol Number	Accurx-001
Sponsor	Accurx, [name]
Purpose	To evaluate the impact of text message support sent to patients from GP practices on self reported symptoms and preventer inhaler adherence for patients with asthma and/or COPD
Study Description	A 6-month randomised controlled trial to evaluate the impact of text message support on symptom control and inhaler adherence for patients with asthma and/or COPD
Number of Study Participants	Approximately 4,000 participants with either asthma and/or COPD (study participants is defined as those who have consented and completed the baseline survey) will be randomly allocated to either the treatment or control group (1:1 ratio)
Study Design	The study is divided into an intervention and control group. Both groups will continue to receive their usual care for the duration of the study. Participants (patients with asthma and/or COPD) who choose to participate will be randomly allocated to either the intervention or control group. Randomisation will be at the individual level. The intervention group will receive a series of supportive text messages over the 6 month trial period, varying in content and frequency. They will also be asked to provide self reported data on their symptoms and their adherence at 3 points in time (start, mid-point, and end of trial). The control group will receive no supportive text messages over the period of the trial. They will be asked to only provide self reported data on their symptoms and their adherence at 3 points in time (start, mid-point, and end of trial).

Protocol: 22 November 2022, v2.0

	For all participants we will analyse prescription data. Both groups will continue to receive their usual standard of care for the duration of the trial.											
Treatment	This is a behavioural intervention. The intervention will consist of a series of supportive text messages over the period of the trial. The messages will vary in frequency from 2 or 3 in the first weeks of the trial to only 1 or 2 a month in the final months of the trial. The content of the messages will vary; some will contain information about how to use a preventer inhaler, some will emphasise the importance of using it, and some will provide simple reminders to patients to take their inhaler.											
Objectives	 Primary objectives: Improved self-reported medication taking as measured by the MARS-5 Questionnaire Secondary objectives: Improved control of asthma symptoms as measured by the Asthma Control Test Improved control of COPD symptoms as measured by the COPD Assessment Test A reduction in the interval between patients requesting preventer inhaler prescriptions Difference in emergency admissions Differences in NHS utilisation 											
Outcome Measurements	 Primary outcome measures: Changes in the MARS-5 Questionnaire from baseline to 13 and 26 weeks Secondary outcome measures: Changes in the Asthma Control Test from baseline to 13 and 26 weeks (for asthma patients) Changes in the COPD Assessment Test from baseline to 13 and 26 weeks (for COPD patients and patients with both asthma and COPD) Reduction in days between consecutive preventer inhaler prescription requests from baseline to 13 and 26 weeks Differences in the number of emergency admissions between the intervention and control group over 26 weeks 											

	Differences in the utilisation of NHS resources between the intervention and control group
Key Inclusion and Exclusion Criteria	Inclusion criteria: Participants eligible for enrollment in the study must meet all the following criteria: 1. Willing and able to provide informed consent and to comply with the study instructions 2. Male and females age 18 or older 3. Confirmed diagnosis of asthma and/or COPD as recorded in the patient's GP medical record 4. Currently prescribed a preventer inhaler 5. Access to a mobile phone 6. Ability to check text messages on phone 7. Ability to read Exclusion criteria: 1. Inability to understand the study procedures 2. Inability or reluctance to provide responses to the study questionnaires 3. Inability to receive and respond to text messages
Key safety arrangement	All participants will continue to receive standard of care for the duration of the trial.
Trial registration	The trial will be registered on the ISRCTN clinical trial registry

3 BACKGROUND AND RATIONALE

3.1 Background

Accurx provides software that allows NHS healthcare teams and patients to seamlessly connect with each other. Through the integrated platform, NHS professionals can manage their patient care and communication. They can use Accurx to send SMS messages and patient questionnaires, provide appointment reminders and referrals, hold video consultations, and manage virtual wards,

outpatient clinics and follow-up pathways.

Accurx's Behaviour Change Team focuses on developing tech solutions which can improve patient outcomes, and medication adherence is one of the focus areas for the team. This focus was chosen based on the high prevalence of asthma and COPD in England, along with the well documented issues in medication adherence in these patients with asthma and/or COPD and the evidence in

support of text message interventions to improve adherence.

3.2 Rationale

Asthma and COPD are lung conditions that affect a considerable proportion of the UK population. Asthma affects around 5.4 million people across the UK,¹ and approximately 1.17 million people in England have been diagnosed with COPD.² Both conditions can have a huge negative impact on patients' quality of life. There are treatments available for both asthma and COPD but research has found controlling these conditions to be a persistent challenge, for example 2.17 million people are

estimated to have uncontrolled asthma in the UK.3

Nonadherence to medication is a major impediment to achieving optimum outcomes in chronic illness. It is estimated that only approximately 50% of medications for chronic disease are taken as prescribed,⁴ and adherence for asthma and COPD medication may be even lower than this.⁵ Research suggests that text message interventions can help improve adherence to medication in patients with a range of conditions including hypertension, diabetes, coronary heart disease, and

asthma.^{6,7,8,9}

Given this evidence around the effectiveness of text message interventions to improve medication adherence, we developed a text message intervention to be sent via the Accurx platform on behalf of a patient's GP practice, supporting them to take their medication as prescribed. All participants will continue to receive their normal standard of care for the duration of the trial.

Protocol: 22 November 2022, v2.0

IRAS ID: 316452

10

4 OBJECTIVES AND OUTCOME MEASURES

4.1 Primary objective and measurement

Objective	Measurement
The primary objective of the trial is to assess the difference in adherence of self-reported	Changes in the MARS-5 Questionnaire from baseline to 13 and 26 weeks will be measured
medication taking as measured by the MARS-5 Questionnaire	in the intervention and control group

4.2 Secondary objectives and measurements

Objectives	Measurement
Improved control of asthma symptoms as measured by the Asthma Control Test	Changes in the Asthma Control Test from baseline to 13 and 26 weeks (for asthma patients)
Improved control of COPD symptoms as measured by the COPD Assessment Test	Changes in the COPD Assessment Test from baseline to 13 and 26 weeks (for COPD patients and patients with both asthma and COPD)
Improved adherence to asthma medication, as indicated by an increase in the frequency with which patients request to refill preventer inhaler prescriptions.	Reduction in the number of days between consecutive preventer inhaler prescription requests from baseline to 13 and 26 weeks
Difference in emergency admissions	Differences in the number of emergency admissions between the intervention and control group over 26 weeks
Differences in NHS utilisation	Differences in the utilisation of NHS resources between the intervention and control group over 26 weeks

The complete survey questionnaire that will be administered to participants can be found in Appendix 7. This appendix includes the full survey questionnaire for (1) asthma and (2) COPD patients, including symptom control as measured through the ACT (for asthma) or CAT (for COPD), medication adherence as measured through the MARS-5 and NHS utilisation questions as measured through a number of questions.

Protocol: 22 November 2022, v2.0

IRAS ID: 316452

11

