7.5 Assessment period

The assessment period will be over a 26 week period. There will be a final survey sent out via text two weeks after the end of the trial (week 28) offering participants in the intervention group only

to provide feedback on the intervention itself via an anonymous survey.

Although assessment will take place over the 26 weeks following the commencement of the

intervention, at weeks 13 and 26 all actively enrolled patients' historical prescription request data

will be accessed, and this data pull will include refill requests dated up to 6 months prior to the

intervention start date.

7.6 **End of Study**

The study will finish for each participant after 26 weeks for the control group and 28 weeks for the

intervention group.

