Hi [name],	Last week we suggested you try and incorporate taking your preventer inhaler into your daily routine. Today take a moment to reflect on how that is going. Have you remembered to take your inhaler more this week now that it is part of a routine?	[Name] [Practice]
Hi [name],	Remember to pick up a new prescription before your preventer inhaler runs out. If you haven't already, you can arrange repeat prescriptions directly with the practice or through your local pharmacy to make things easier.	Thanks, [Name] [Practice]
Hi [name],	Are you finding these messages useful? Let us know by answering two quick questions via the link below. Please complete this questionnaire: [GOOGLE FORM] If you no longer want to receive the messages, you can opt out at [link to opt out].	Many thanks, [Name] [Practice]
Hi [name],	You can reduce the risk of symptoms like wheezing, breathlessness and a tight chest by using your preventer inhaler every day.	[Name] [Practice]
	Please use your inhaler today if you haven't already.	
Good morning [name],	Have you taken your preventer inhaler yet today? Please remember to take it if you haven't already.	Thanks, [Name] [Practice]
Hi [name],	Asthma flare ups can have a negative impact on your day-to-day life. Using your preventer inhaler today - and every day - lets you gain greater control of your symptoms to help avoid these flare-ups.	[Name] [Practice]
	If you haven't already, please use your inhaler today.	
Hi [name],	Some people tell us that they mean to use their inhaler every day but simply forget. If you struggle with this too, try keeping it somewhere where you'll see it every day, such as by your toothbrush, next to the kettle, or on your bedside table.	Thanks, [Name] [Practice]
Hi [name],	Hopefully you're finding that your asthma is better controlled now that you've been taking your preventer inhaler regularly. We know that many patients find it difficult to remember to take their preventer inhaler when their symptoms improve, but please try to keep taking it as prescribed to help stop your symptoms getting worse and reduce the risk of a flare-up.	Thanks, [Name] [Practice]
Hi [name],	We've been sending you these messages for 3 months now, and we hope that you're finding them helpful. Please answer the short questionnaire below about your asthma to help us understand your symptoms and how you're using your preventer inhaler. Please complete this questionnaire: florey.url ACT/CAT	Many thanks, [Name] [Practice]

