Good morning [name],	Make sure your asthma is well-controlled by using your preventer inhaler today - and every day. Remember that if you no longer want to receive the messages, you can opt out at [link to opt out].	Thanks, [Name] [Practice]

Hi [name],	Remember that you need to take your preventer inhaler every day. Taking your inhaler every day will reduce your risk of experiencing asthma symptoms and help build up protection in your airways over time.	Thanks, [Name] [Practice]
Hi [name],	Your preventer inhaler is designed to prevent asthma symptoms. It's important to use it every day, as prescribed, and not only when you experience asthma symptoms.	[Name] [Practice]
	Please try to take it even when your asthma doesn't feel particularly bad.	
Hi [name],	Please remember to take your inhaler today if you haven't taken it yet. By taking your preventer inhaler today - and every day - you are helping to keep your asthma under control.	Thanks, [Name] [Practice]
Good morning [name],	Don't forget to pick up a new prescription before your preventer inhaler runs out. If you haven't already, you can arrange repeat prescriptions with your local pharmacy to make things easier.	Thanks, [Name] [Practice]
Good morning [name],	Just a quick reminder to take your inhaler today if you haven't already. Using your inhaler regularly helps us keep your asthma under control.	Thanks, [Name] [Practice]
Hi [name],	You've now received these messages for the past 6 months. Please let us know how you're feeling by answering the short questionnaire below about your asthma. It should only take you 3 minutes and it will really help us to understand whether these reminders benefit patients.	Many thanks, [Name] [Practice]
	Please complete this questionnaire: florey.url ACT/CAT	
Hi [name],	Final step! Tell us how you found receiving messages from us at Accurx on behalf of your GP practice over the last 6 months. Please could you take 2 minutes to share your feedback through the anonymous survey link below? The deadline for completing the survey is [date].	Thanks, [name] accuRx
	[survey link]	
	Thank you for taking part in this study. This is the last text message we'll be sending you as part of the study.	

COPD - i	COPD - intervention group							
Hi [name],	Thanks for signing up to take part in the study about your breathing condition - COPD. You'll receive your first message from us in the next few days.							

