Hi [name],	Do you take your inhaler as part of a routine? Many patients find that incorporating it into their daily routine can help them remember to take it.	Many thanks, [Name] [Practice]
	If you think this might help you, you could try taking your inhaler before you brush your teeth every day.	
Hi [name],	Just a quick reminder to use your inhaler today if you haven't already. By using your regular inhaler every day, you are helping better control your COPD symptoms.	[Name] [Practice]
Hi [name],	Last week we suggested you try and incorporate taking your preventer inhaler into your daily routine. Today, take a moment to reflect on how that is going. Have you remembered to take your inhaler more this week now that it is part of a routine?	[Name] [Practice]
Hi [name],	Remember to pick up a new prescription before your regular inhaler runs out. If you haven't already, you can arrange repeat prescriptions directly with the practice or through your local pharmacy to make things easier.	Thanks, [Name] [Practice]

	 	
Hi [name],	Are you finding these messages useful? Let us know by answering two quick questions via the link below.	Many thanks, [Name] [Practice]
	Please complete this questionnaire: [GOOGLE FORM]	[[]
	If you no longer want to receive the messages, you can opt out at [link to opt out].	
Hi [name],	You can reduce the risk of symptoms like wheezing, breathlessness and a tight chest by using your regular inhaler every day.	[Name] [Practice]
	Please use your inhaler today if you haven't already.	
Good morning [name],	Have you taken your regular inhaler yet today? Please remember to take it if you haven't already.	Thanks, [Name] [Practice]
Hi [name],	COPD flare-ups can have a negative impact on your day-to-day life. Using your inhaler today - and every day - lets you gain greater control of your symptoms to help avoid these flare-ups.	[Name] [Practice]
	If you haven't already, please use your inhaler today.	
Hi [name],	Some people tell us that they mean to use their inhaler every day but simply forget. If you struggle with this too, try keeping it somewhere where you'll see it every day, such as by your toothbrush, next to the kettle, or on your bedside table.	Thanks, [Name] [Practice]
Hi [name],	Hopefully you're finding that your COPD is better controlled now that you've been taking your regular inhaler more often.	Thanks, [Name] [Practice]

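### Any shorter gap between preventer requests is scored as better adherence, with no link to supply, while only the intervention arm is texted to renew its prescription

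*Protocol*

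**What the plan says.** Protocol section 4.2 gives the objective as "Improved adherence to asthma medication, as indicated by an increase in the frequency with which patients request to refill preventer inhaler prescriptions" and the measurement as "Reduction in the number of days between consecutive preventer inhaler prescription requests from baseline to 13 and 26 weeks". The synopsis has the same outcome: "Reduction in days between consecutive preventer inhaler prescription requests from baseline to 13 and 26 weeks". Section 7.5 describes the source as request records extracted at weeks 13 and 26, and says "this data pull will include refill requests dated up to 6 months prior to the" intervention start date. Nowhere is this outcome tied to quantity issued, prescribed dose, days of supply or number of preventer products.

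Appendix 4 sends the intervention arm two texts about renewing prescriptions. For asthma, the first says "Remember to pick up a new prescription before your preventer inhaler runs out" and adds "you can arrange repeat prescriptions directly with the practice or through your local pharmacy to make things easier"; the second says "Don't forget to pick up a new prescription before your preventer inhaler runs out". The COPD set has the same pair, the first being "Remember to pick up a new prescription before your regular inhaler runs out". Appendix 6 has no such text for the control arm.

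**The concern.** The protocol fixes both the metric, calendar days between requests, and its direction, fewer days being better. A patient who orders while still holding stock is then recorded as more adherent with no change in use. The prompt to order goes to one arm only, so the intervention acts directly on the timing of the event being measured.

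This matters because prescription requests are the only outcome taken from records. By section 10.1 and Appendix 7, MARS-5, ACT, CAT, admissions and NHS use all come from the participant survey. Intervention patients know that they are receiving texts, so the refill outcome is the natural check on self-report. As defined, it cannot separate closing a real gap in supply from ordering early.

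There is also a mismatch of scope. The objective in 4.2 names asthma medication only, while the synopsis and section 10.1 take prescription data for all participants, and the inhaler-prescription row in Appendix 2 has no disease restriction.

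**Working it through.** The protocol gives no effect size, SD or power for this outcome, so there is no stated figure to reproduce. It gives no pack size either. The 30-day inhaler, the size of the shift, the share responding and the SDs below are assumptions.

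**Timing of the prompts.** The week 13 and week 26 ticks in Appendix 3 line up with the 3-month and 6-month questionnaires in Appendix 4 if the first tick is the baseline questionnaire. On that count the two prescription texts fall in about weeks 7 and 23, before the week 13 and week 26 extractions respectively. The second comes about three weeks before the final extraction. With a 30-day inhaler, a compensating longer gap would often be incomplete by then.

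**Effect of one early request, use unchanged.** Mean gap = (last request date − first request date) / number of gaps. Bringing one request forward by e days over k gaps, with no later compensation, lowers the mean by e/k. For e = 5:
- 13 weeks, k = 3: 5/3 = 1.7 days; k = 2: 5/2 = 2.5 days.
- 26 weeks, k = 6: 5/6 = 0.8 days for one early request; 10/6 = 1.7 days if both texts each bring a request forward 5 days.
- For shifts of 3, 7 and 14 days over 3 gaps: 1.0, 2.3 and 4.7 days.

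**A real change, for comparison.** Raising adherence from 80% to 85% moves the gap from 30/0.80 = 37.5 to 30/0.85 = 35.3 days, a fall of 2.2 days. Within one patient, the artefact is of the same order.

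**Between arms.** Multiply by the share who act on the text. At 20%, the 13-week effect is 0.20 × 1.7 = 0.3 to 0.20 × 2.5 = 0.5 days. At 26 weeks, one early request gives 0.20 × 0.8 = 0.2 days.

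**Against what the trial could detect.** Detectable difference = SD × √(2/n) × (1.960 + 0.842), at two-sided 5% and 80% power. For SDs of 10 to 30 days it is 2.0 to 5.9 days with 400 per arm and 1.0 to 3.0 days with 1,600 per arm. With 5-day shifts at 13 weeks, the artefact reaches 1.0 day only if 1.0/2.5 = 40% to 1.0/1.7 = about 60% of the arm respond.

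**Changes not tied to arm.** Doubling the puffs from the same device moves the gap from 30 to 15 days. Two 30-day preventers requested 15 days apart give 15 days if requests are counted across products. Two inhalers per request move it from 30 to 60 days and score as worse. If 5% to 10% of patients have a 15-day change, the added SD is 15 × √(0.05 × 0.95) = 3.3 to 15 × √(0.10 × 0.90) = 4.5 days. Adding 4.5 in quadrature takes an SD of 10 to 11.0 and an SD of 30 to 30.3, a rise of about 10% down to 1%.

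**The case against.** The texts ask patients to renew before running out, not to stockpile. Section 3.2 puts adherence for chronic medication at about 50%, possibly lower in asthma and COPD. For patients who do run out, a timely request closes a real gap and is an intended benefit. That stands. The artefact is confined to requests made with stock in hand, and it shrinks with the share who respond, with more gaps in the average, and with any later compensating request.

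A reader might infer that dose increases and second inhalers also favour the intervention. The documents do not support this. Both arms continue usual care and are randomised, so such changes should be roughly balanced and can move the gap either way. A dose increase shortens the gap only if the device empties faster. Counting requests across products is allowed by the wording but not stated. A reader might also think of inhalers used for both daily and relief treatment; the protocol describes none, and its texts separate the daily inhaler from a reliever.

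The unseen SAP may add rules for products and quantities. It could not change the metric or its direction without departing from section 4.2.

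Finally, a supply ratio is not immune to prompting. Over 91 days, two 30-day requests give 60/91 = 66% and three give 90/91 = 99%, so a request pulled inside the window still raises the ratio, and a 100% cap alone does not prevent it. This is why the fix needs a carry-forward rule and a stated limit on interpretation.

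**Conclusion.** The point holds in a limited form. The refill outcome credits any shorter gap, and the arm-specific texts can shorten it without extra inhaling. The size is 1.7 to 2.5 days per responding patient over 2 to 3 gaps and about 0.8 days over 6 gaps for one early request. Between arms it is 0.3 to 0.5 days at 13 weeks if 20% respond. These figures assume a 30-day inhaler, a 5-day shift and no compensating later request.

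It would be wrong to read 1.7 to 2.5 days as the expected difference between arms; that needs every intervention patient to respond. Regimen, pack-size and product changes are mainly a source of noise. The outcome is secondary and the MARS-5 primary is unaffected, but the definition should be changed because this is the one outcome not taken from self-report.

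**What to change.** In section 4.2 and the synopsis:
- Define the outcome as days of preventer supplied divided by days elapsed, per product, using the quantity and prescribed dose in the planned record extraction. Average across a patient's products and cap at 100%.
- Carry supply from an early request forward instead of crediting it to the current period.
- Describe the outcome as medicine supply, not inhaler taking. State that the refill texts act directly on request timing, which the measure cannot fully separate from adherence in patients below 100%.
- Keep the raw gap between requests as a descriptive result.
- State that the outcome covers both asthma and COPD.

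The cost is wording in the protocol and SAP, some coding of dose instructions, and confirming that quantity and dose fields can be extracted, since the protocol does not list the fields. Some records may have no usable quantity.
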